# 12.1.7 Monitoring and Auditing

All source data must be accessible for auditing and monitoring. Monitors and auditors will maintain patient confidentiality.

Monitoring will be periodically performed during the study, to ensure that GCP and all aspects of the protocol are followed. The monitoring frequency will be adapted to patient accrual of trial sites. As further defined in the monitoring plan, monitoring of trial data can be done either on-site or by central review of anonymous source data. The investigators/ their institutions guarantee access to source documents by the monitor and appropriate regulatory agencies.

Patient source documents are the physician's patient records maintained at the study site. Generally, source documentation will be the hospital's or the physician's chart. In these cases, the information collected on the case report form must match source documentation.

The trial site may also be subject to quality assurance audit by PIQUR as well as inspection by appropriate regulatory agencies.

It is important that the investigator and the relevant personnel are available during the monitoring visits and possible audits and that sufficient time is devoted to the process.

Authorities have the right to perform inspections, and the sponsor has the right to perform onsite auditing during working hours upon reasonable prior notice.

# 12.1.8 Ongoing review of data

As this is an open label single-arm study, and as the currently known risks to trial participants are relatively well manageable, a formal independent Data Monitoring Committee is considered not needed. However, ongoing review of safety and efficacy data will be performed at regular intervals (at least once every 2 months) by the principal investigator, representatives of the sponsor (Chief Medical Officer and Drug Safety Officer), and an experienced physician not directly involved in the conduct of the trial. Data to be reviewed will include adverse events reported, laboratory abnormalities, answers to the patient questionnaires, as well as tumor response data. Reviewed data and meeting minutes will be stored in the TMF.

# 12.1.9 Study and site closure

PIQUR reserves the right to discontinue this study under the conditions specified in the clinical study agreement.

# **12.1.10 Publication policy**

PIQUR is committed to following high ethical standards for reporting study results for its innovative medicine, including the timely communication and publication of clinical trial results, whatever their outcome. PIQUR assures that the key design elements of this protocol will be posted in a publicly accessible database, e.g. such as www.clinicaltrials.gov, before

study start. Within 1 year of upon study completion (i.e., last patient last visit) and finalization of the study report, the results of this study will be submitted for publication by PIQUR.

Authors will not receive remuneration for their writing of a publication, either directly from PIQUR or through the professional medical writing agency. Author(s) may be requested to present poster or oral presentation at scientific congress; however, there will be no honorarium provided for such presentations.

As part of its commitment to full transparency in publications, PIQUR supports the full disclosure of all funding sources for the study and publications, as well as any actual and potential conflicts of interest of financial and non-financial nature by all authors, including medical writing/editorial support, if applicable.

# 12.2 Appendix 2: Adverse Events: definitions, assessment, follow-up, and reporting

# 12.2.1 AE Definition

An AE is any untoward medical occurrence in a patient, temporally associated with the use of an investigational medicinal product (IMP, bimiralisib), whether or not considered related to the IMP.

An AE can therefore be any unfavorable and unintended sign (including an abnormal laboratory finding), symptom, or disease (new or exacerbated) temporally associated with the use of IMP.

# **12.2.1.1** Events meeting the AE definition:

- Any abnormal laboratory test results (hematology, clinical chemistry, or urinalysis) or other safety assessments (eg, ECG, radiological scans, vital signs measurements), including those that worsen from baseline, considered clinically significant in the medical and scientific judgment of the investigator.
- Exacerbation of a chronic or intermittent pre-existing condition including either an increase in frequency and/or intensity of the condition.
- New conditions detected or diagnosed after IMP administration even though it may have been present before the start of the study.
- Signs, symptoms, or the clinical sequelae of a suspected drug-drug interaction.
- Signs, symptoms, or the clinical sequelae of a suspected overdose of either IMP or a concomitant medication. IMP overdose per se will not be reported as an AE/SAE unless it is an intentional overdose taken with possible suicidal/self-harming intent. Such overdoses should be reported regardless of sequelae.
- "Lack of efficacy" or "failure of expected pharmacological action" per se is not considered an AE. Such instances will be captured in the efficacy assessments. However, symptomatic disease progression (signs, symptoms, and/or clinical sequelae resulting from lack of efficacy) will be reported as AE if they fulfil the definition of an AE.

# 12.2.1.2 Events NOT meeting the AE definition

- Any clinically significant abnormal laboratory findings or other abnormal safety assessments which are associated with the underlying disease, unless judged by the investigator to be more severe than expected for the participant's condition.
- Asymptomatic disease progression
- Medical or surgical procedure (eg, endoscopy, appendectomy): the condition that leads to the procedure is the AE.

- Situations in which an untoward medical occurrence did not occur (social and/or convenience admission to a hospital).
- Anticipated day-to-day fluctuations of pre-existing disease(s) or condition(s) present or detected at the start of the study that do not worsen.

### **12.2.2 SAE Definition**

If an event is not an AE per definition above, then it cannot be an SAE even if serious conditions are met

### A SAE is defined as any untoward medical occurrence that, at any dose:

#### a. Results in death

### b. Is life-threatening

The term 'life-threatening' in the definition of 'serious' refers to an event in which the participant was at risk of death at the time of the event. It does not refer to an event, which hypothetically might have caused death, if it were more severe.

### c. Requires inpatient hospitalization or prolongation of existing hospitalization

In general, hospitalization signifies that the participant has been detained (usually involving at least an overnight stay) at the hospital or emergency ward for observation and/or treatment that would not have been appropriate in the physician's office or outpatient setting. Complications that occur during hospitalization are AEs. If a complication prolongs hospitalization or fulfills any other serious criteria, the event is serious. When in doubt as to whether "hospitalization" occurred or was necessary, the AE should be considered serious.

Hospitalization for elective treatment of a pre-existing condition that did not worsen from baseline is not considered an AE.

### d. Results in persistent disability/incapacity

- The term disability means a substantial disruption of a person's ability to conduct normal life functions.
- This definition is not intended to include experiences of relatively minor medical significance such as uncomplicated headache, nausea, vomiting, diarrhea, influenza, and accidental trauma (e.g. sprained ankle) which may interfere with or prevent everyday life functions but do not constitute a substantial disruption.

#### e. Is a congenital anomaly/birth defect

f. Other situations:

• Medical or scientific judgment should be exercised in deciding whether SAE reporting is appropriate in other situations such as important medical events that may not be immediately life-threatening or result in death or hospitalization but may jeopardize the participant or may require medical or surgical intervention to prevent one of the other outcomes listed in the above definition. These events should usually be considered serious.

Examples of such events include invasive or malignant cancers, intensive treatment in an emergency room or at home for allergic bronchospasm, blood dyscrasias or convulsions that do not result in hospitalization, or development of drug dependency or drug abuse.

# 12.2.3 Assessment, documentation and follow-up of AE

When an AE occurs, it is the responsibility of the investigator to review all available relevant documentation (e.g. hospital progress notes, laboratory reports, and diagnostics reports) related to the event.

The investigator will attempt to establish a diagnosis of the event based on signs, symptoms, and/or other clinical information. Whenever possible, the diagnosis (not the individual signs/symptoms) will be documented as the AE and recorded in the CRF.

### 12.2.3.1 Assessment of Intensity

The investigator will make an assessment of intensity for each AE and assign it to one of the following categories, and where appropriate, in accordance with the CTCAE criteria version 5.0:

Grade 1 (Mild): An event that is easily tolerated by the participant, causing minimal discomfort and not interfering with everyday activities.

Grade 2 (Moderate): An event that causes sufficient discomfort and interferes with normal everyday activities.

Grade 3 (Severe): An event that prevents normal everyday activities. An AE that is assessed as severe should not be confused with a SAE. Severe is a category utilized for rating the intensity of an event; and both AEs and SAEs can be assessed as severe.

An event is defined as 'serious' when it meets at least 1 of the predefined outcomes as described in the definition of an SAE, NOT when it is rated as severe.

# 12.2.3.2 Assessment of Causality

The investigator is obligated to assess the relationship between IMP and each occurrence of each AE. The assessment will be either "related" or "unrelated".

A "reasonable possibility" of a relationship conveys that there are facts, evidence, and/or arguments to suggest a causal relationship, rather than a relationship cannot be ruled out.

The investigator will use clinical judgment to determine the relationship.

Alternative causes, such as underlying disease(s), concomitant therapy, and other risk factors, as well as the temporal relationship of the event to IMP administration will be considered and investigated.

The investigator will also consult the Investigator's Brochure (IB) and/or Product Information, for marketed products, in his/her assessment.

For each AE, the investigator must document in the medical notes that he/she has reviewed the AE and has provided an assessment of causality.

# 12.2.4 Reporting of SAEs

Safety information is to be reported to Precision Safety until 31 January 2020 at 23:59 CET.

Safety information is to be reported to **PRA Health Sciences** from 01 February 2020 at 00:00 CET onwards.

**Initial Reporting:** Within 24 hours of becoming aware of a serious adverse event (SAE):

- Complete the AE eCRF indicating the event is serious
- Complete the eCRFs for the patient (Demographics, Medical History, Concomitant Medications)
- E-mail de-identified available source documentation (i.e., discharge summary) to Precision Safety or PRA Health Sciences (see above), ensuring patient number and protocol number are included on all documents
- Submit the SAE notification to your local IRB, as required

**Only** if the EDC system is unavailable, immediately:

- Fax the following documents to Precision Safety or PRA Health Sciences
  - Completed back-up paper SAE Report Form. The following fields must be completed before sending: "Patient identification," "Site identification," "Event term," "Relationship to study drug," and "Serious criteria"
- Enter the SAE into EDC system within 24 hours of the system becoming available

#### From 01 February 2020, at 00:00 CET

PRA Health Sciences email: [contact] PRA Health Sciences [contact]

Initial notification via telephone or email does not replace the need for the investigator to provide a completed SAE report form within the designated reporting time frames.

There may be instances when copies of medical records for certain cases are requested by the sponsor. In this case, all participant identifiers, with the exception of the patient number, will be redacted on the copies of the medical records before submission to the sponsor.

There may be situations in which an SAE has occurred and the investigator has minimal information to include in the initial report to the sponsor. However, it is very important that the investigator always make an assessment of causality for every event before the initial transmission of the SAE data to the sponsor.

The investigator may change his/her opinion of causality in light of follow-up information and send a SAE follow-up report with the updated causality assessment.

The causality assessment is one of the criteria used when determining regulatory reporting requirements.

#### 12.2.5 Follow-up of SAEs

The investigator is obligated to perform or arrange for the conduct of supplemental measurements and/or evaluations as medically indicated or as requested by the sponsor to elucidate the nature and/or causality of the SAE as fully as possible. This may include additional laboratory tests or investigations, histopathological examinations, or consultation with other health care professionals.

If a participant dies during participation in the study or during a recognized follow-up period, the investigator will provide the sponsor with a copy of any post-mortem findings including histopathology.

The investigator will submit any updated SAE data to the sponsor within 24 hours of awareness. The investigator will re-assess causality whenever submitting SAE follow-up information.

#### **Follow-up Reporting:**

- Update EDC within 24 hours of receipt of new information and fax or email available source documents to Precision Safety or PRA Health Sciences
  - If EDC is unavailable, complete the back-up paper *SAE Report Form* and fax or email to Precision Safety or PRA Health Sciences

# **12.3** Appendix 3: Criteria for definition of women with childbearing potential and guidance on contraception methods

#### **12.3.1** Female patients with childbearing potential are defined as follows:

- Patients with regular menses
- Patients, after menarche with amenorrhea, irregular cycles, or using a contraceptive method that precludes withdrawal bleeding
- Women who underwent tubal ligation 1 year or more prior to consent signature

# **12.3.2** Female patients may be considered to NOT be of childbearing potential for the following reasons:

- The patient has undergone total abdominal hysterectomy with bilateral salpingo-oophorectomy or bilateral oophorectomy
- The patient is medically confirmed to be menopausal (no menstrual period) for 24 consecutive months

#### **12.3.3** Guidance on contraception methods

# (adapted from the '*Recommendations related to contraception and pregnancy testing in clinical trials*', Clinical Trials Facilitation Group, 15 September 2014) for women of childbearing potential

Methods that can achieve a failure rate of less than 1% per year when used consistently and correctly are considered as highly effective birth control methods.

Patients should use a highly effective contraceptive measure from the list below. This requirement is valid for female patients with childbearing potential, as well as female partners with childbearing potential of male patients.

• Combined (estrogen and progestogen containing) hormonal contraception associated with inhibition of ovulation  :

o oral

o intravaginal

o transdermal

• Progestogen-only hormonal contraception associated with inhibition of ovulation  :

o oral

o injectable

o implantable

- Intrauterine device (IUD)
- intrauterine hormone-releasing system (IUS)

- bilateral tubal occlusion 
- vasectomised partner 
- sexual abstinence. 

Hormonal contraception may be susceptible to interaction with the IMP, and can thus NOT be used alone as method of contraception

Contraception methods that are considered to have low user dependency.

Vasectomised partner is a highly effective birth control method provided that partner is the sole sexual partner of the trial participant and that the vasectomised partner has received medical assessment of the surgical success.

 Sexual abstinence is considered a highly effective method only if defined as refraining from heterosexual intercourse during the entire period of risk associated with the study treatments. The reliability of sexual abstinence needs to be evaluated in relation to the duration of the clinical trial and the preferred and usual lifestyle of the subject.

# **Unacceptable methods of contraception for women of childbearing potential:**

Birth control pills without oestrogen Intrauterine device progesterone T Female condom Natural family planning (i.e., rhythm method) or breastfeeding Fertility awareness Withdrawal Cervical shield.

# **12.4** Appendix 4: ECOG performance status

### SCORE

- 0 Able to carry out all normal activity without restriction.
- 1 Restricted in physically strenuous activity but ambulatory and able to carry out light work.
- 2 Ambulatory and capable of all self-care but unable to carry out any work; up and about more than 50% of waking hours.
- 3 Capable of only limited self-care; confined to bed or chair more than 50% of waking hours.
- 4 Completely disabled; cannot carry on any self-care; totally confined to bed or chair.

# **12.5** Appendix 5: Patient Reported Questionnaires

# Table 4:PHQ-9 Depression Scale

Over the last 2 weeks , how often have you been bothered by any of the following problems?	Not at all	Several days	More than	Nearly every
(Use "√" to indicate your answer)			half the days	day
1. Little interest or pleasure in doing things	0	1	2	3
2. Feeling down, depressed, or hopeless	0	1	2	3
3. Trouble falling or staying asleep, or sleeping too much	0	1	2	3
4. Feeling tired or having little energy	0	1	2	3
5. Poor appetite or overeating	0	1	2	3
6. Feeling bad about yourself – or that you are a failure or have let yourself or your family down	0	1	2	3
7. Trouble concentrating on things, such as reading the newspaper or watching television	0	1	2	3
8. Moving or speaking so slowly that other people could have noticed? Or the opposite – being so fidgety or restless that you have been moving around a lot more than usual	0	1	2	3
9. Thoughts that you would be better off dead or of hurting yourself in some way	0	1	2	3
For Office Coding		 	ł	+
	= Total Sc	ore:		

If you checked off **any** problems, how **difficult** have these problems made it for you to do your work, take care of things at home, or get along with other people?

Not difficult	Somewhat	Very	Extremely
at all	difficult	difficult	difficult

For information purposes only

Over the last 2 weeks, how often have you been bothered by the following problems? (Use " $$ "to indicate your answer)	Not at all	Several days	More than half the days	Nearly every day
1. Feeling nervous, anxious or on edge	0	1	2	3
2. Not being able to stop or control worrying	0	1	2	3
3. Worrying too much about different things	0	1	2	3
4. Trouble relaxing	0	1	2	3
5. Being so restless that it is hard to sit still	0	1	2	3
6. Becoming easily annoyed or irritable	0	1	2	3
7. Feeling afraid as if something awful might happen	0	1	2	3
(For office coding: Total Score T		=	+)	+

Table 5:GAD-7 Anxiety Scale

For information purposes only

# 12.6 Appendix 6: recommendations for the management of specific safety events

# **12.6.1** Recommendations for management of hyperglycemia

The PI3K/AKT pathway is important in regulating glucose metabolism, particularly by regulating glucose transport into adipocytes and muscle tissue. Therefore, hyperglycaemia is considered to be an "on-target" effect of bimiralisib, and it has been commonly observed in patients treated with bimiralisib so far. Contrary to regular type 2 diabetes, bimiralisib-induced hyperglycemia may present with a rapid onset on high fasting plasma glucose (FPG) peaks.

In order to mitigate the risk of developing uncontrolled hyperglycaemia on PQR309 treatment, only patients with  $FPG \le 150 \text{ mg/dL}$  are eligible for study entry. In addition, vigilant monitoring of patients is recommended including: regular monitoring of FPG to identify hyperglycaemia at an early stage and prevent acute/sub-acute complications. Particular caution is warranted if a patient presents any of the following:

- (family) with history of diabetes mellitus
- borderline fasting glucose (126 mg/dL or higher)
- impaired fasting glucose
- obesity
- patient receiving corticosteroids
- other severe medical conditions (e.g. infections).

For patients concerned by any of the above, it may be necessary to measure FPG more frequently than indicated in the "Schedule of Assessments" (Table 4), e.g. daily, or as clinically indicated. In addition, a home glucometer may be provided to patients to monitor blood glucose levels at home in between study visits.

Hyperglycemia management guidance should also include dietetic measures: patients should be advised about appropriate diet to minimize risk and facilitate management of hyperglycemia.

If a patient develops hyperglycaemia with FPG levels above the "upper limit of normal" (ULN), FPG must be monitored more frequently, e.g. daily with a home glucometer, or as clinically indicated until resolved to < ULN. Importantly any FPG value used for treatment-relevant decisions has to be confirmed by two consecutive measurements performed by a certified laboratory. Once hyperglycemia has resolved, FPG monitoring should be continued as clinically indicated.

If FPG levels rise above ULN, it is advised to initiate or intensify therapy preferably with oral medication. Inhibitors of the Sodium-glucose linked –transporter -2 (SGLT2) (e.g. canagliflozin

(InvokanaTM) are recommended, as they generally show effect within 1-2 days. Patients treated with SGLT2 inhibitors should closely be monitored for signs or symptoms of ketoacidosis.

If SGLT2 inhibitors are not available or contra-indicated (e.g. in patients with renal impairment), metformin should be used. Sulfonylureas should be avoided because of their mechanism of action.

If FPG levels cannot be reduced to < 13.9 mmol/L (250 mg/dL) with adequate anti-diabetic treatment within two consecutive days, treatment with insulin should be initiated or intensified. It is advised to use long-acting insulin, e.g. TresibaTM, starting with 8 units and increasing every 3 days by 2 units if necessary. If target glucose control is not reached continue escalation after 3 day evaluations.

If a patient interrupts or discontinues PQR309 treatment while on anti-diabetic medication, he/she has to be monitored vigilantly for signs or symptoms of **hypo**glycaemia.

PQR309 treatment should be continued as long as hyperglycaemia is controlled. If hyperglycaemia is not controlled (defined as FPG > 13.9 mmol/L (250 mg/dL) for more than two consecutive days) despite adequate intervention, therapy with PQR309 should be interrupted. Re-start of PQR309 treatment can be considered once FPG levels are controlled and maintained at < 9.0 mmol/L (160 mg/dL) with adequate medication. Conditions for PQR309 treatment restart including dosing are provided in Section 12.6.1.1.

A graphical representation of these guidelines is shown in Figure 3.

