### 7.2 Treatment interruptions and bimiralisib dose reductions

For patients who do not tolerate the protocol-specified dose, dose adjustments are permitted in order to allow the patient to continue bimiralisib treatment. Changes in dosing schedule are not allowed. Any changes in bimiralisib administration must be recorded on the CRF. Whenever possible, any dose adjustment of bimiralisib should be discussed between the investigator and the study sponsor prior to implementation.

As a first step to manage bimiralisib-related toxicities, bimiralisib treatment should be temporarily interrupted.

All treatment interruptions, discontinuations and dose reductions must be based on the worst preceding AE as graded by the NCI common terminology criteria for AE (NCI-CTCAE version 5.0). Once the bimiralisib dose has been reduced, re-escalation is not permitted.

Guidelines for treatment interruptions and bimiralisib dose reductions are described in Table 4.

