#### Figure 3: General Treatment Guidelines for Hyperglycaemia

**Fasting Glucose (FPG):** analyses to be performed by certified laboratory; hyperglycemia has to be confirmed by two consecutive measurements

G1/2	
 
dietary advice
 
start with or intensify oral anti-diabetics SGLT2 inhibitors recommended*
 

> ULN - < 13.9 mmol/L	
> ULN - < 250 mg/dL	continue with PQR309 treatment at the same dose

G3/4	Interrupt PQR309 treatment
≥ 13.9 mmol/L	Interrupt 1 QKS09 treatment
≥ 250 mg/dL	Initiate or intensify insulin therapy
for > 2 days	(long-acting insulin is recommended)

**Re-starting PQR309:** *PQR309 may be restarted if FPG controlled below 9 mmol/L (160 mg/dL) for two consecutive days; additional conditions and PQR309 dose restrictions apply for restart (see section 10.8.2)* 

\* If not available or counter-indicated (e.g. for patients with renal impairment), metformin should be used. Sulfonylureas should not be used because of their mechanism of action.

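### Appendix 6 states no immediate hold at the protocol's own Grade 4 glucose level (above 500 mg/dL), so handling of a short Grade 4 peak is ambiguous

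*Protocol*

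**What the plan says.** All places are in the protocol; the SAP sections supplied cover only hypotheses and sample size.

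- **Section 12.6.1, default.** "PQR309 treatment should be continued as long as hyperglycaemia is controlled". Glucose counts as not controlled only when FPG stays above 250 mg/dL (13.9 mmol/L) "for more than two consecutive days) despite adequate intervention, therapy with PQR309 should be interrupted".
- **Section 12.6.1, insulin.** If FPG cannot be brought below 250 mg/dL "within two consecutive days, treatment with insulin should be initiated or intensified".
- **Section 12.6.1, confirmation.** An FPG value used for a treatment decision "has to be confirmed by two consecutive measurements performed by a certified laboratory".
- **Figure 3.** One row covers Grades 3 and 4: 250 mg/dL or more for over two days leads to interruption and insulin. No row covers 250 mg/dL or more lasting two days or less. For restart, "additional conditions and PQR309 dose restrictions apply for restart (see section 10.8.2"; the protocol has no such section. The text of 12.6.1 correctly points to 12.6.1.1.
- **Section 12.6.1.1.** Grade 4 is above 500 mg/dL (27.8 mmol/L). The section says when a patient may restart or must discontinue, but not when the hold begins.
- **Section 7.2.** "As a first step to manage bimiralisib-related toxicities, bimiralisib treatment should be temporarily interrupted". Interruptions must follow the worst preceding CTCAE grade. Table 4, which stops drug permanently for other non-haematological Grade 4 events, excludes hyperglycaemia in its title.

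**The concern.** Hyperglycaemia is an important identified risk, reported in almost half of exposed patients (Section 4.5.2.8). Section 12.6.1 warns that on this drug it "may present with a rapid onset on high fasting plasma glucose (FPG) peaks". A trigger that needs more than two days suits a fast, high peak least well. Section 4.4 says exposure builds up over the two dosing days, so a second dose given after a warning value adds to it.

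The protocol itself treats Grade 4 as the more serious event. A Grade 3 episode that settles within 14 days may restart at the same dose, whereas a Grade 4 episode may restart only at the reduced dose. Yet a Grade 4 peak of two days or less never meets the stated hold trigger, so it is unclear whether the Grade 4 restart rules apply to it. One site could continue at 140 mg while another holds and moves the patient to 100 mg for good. What is at stake is patient safety and consistency between sites.

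**Working it through.** **Unit check.** Dividing mg/dL by 18.016 gives 250 → 13.88, 500 → 27.75 and 160 → 8.88 mmol/L. The protocol prints 13.9, 27.8, and 8.9 or 9.0. The thresholds are internally consistent apart from that rounding.

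**Rules side by side.**

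| Place | Level | Duration needed | Action |
|---|---|---|---|
| 7.2, Table 4 | Grade 4 non-haematological event | none | stop permanently; hyperglycaemia excluded |
| 7.2, text | any related toxicity | not stated | interrupt first, by worst preceding grade |
| 12.6.1 | FPG > 250 mg/dL | more than two days | interrupt |
| Figure 3, G3/4 row | FPG ≥ 250 mg/dL | more than two days | interrupt, insulin |
| 12.6.1.1, G4 | FPG > 500 mg/dL | none given for starting a hold | restart and discontinuation rules only |
| 9.10 | unacceptable event or physician decision | none | withdraw from treatment |

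No row joins the 500 mg/dL level to an immediate hold.

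**Doses before the trigger, read literally.** Doses fall on days 1 and 2 of each 7-day block (Section 7.1). Let FPG first exceed 500 mg/dL on block day *d* and stay above 250 mg/dL. Assume a fasting pre-dose value every day; the protocol offers daily checks only as an example. The count is the number of dosing days from *d* up to the day before the hold. The hold falls on *d* + 2 if the third daily value meets the condition, or on *d* + 3 if a full 48 hours must be exceeded.

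| Onset day *d* | Hold on *d* + 2 | Hold on *d* + 3 |
|---|---|---|
| 1 | 2 | 2 |
| 2 | 1 | 1 |
| 3, 4, 5 | 0 | 0 |
| 6 | 0 | 1 |
| 7 | 1 | 2 |

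The proviso about adequate intervention and the two-value laboratory rule could lengthen the wait.

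**What an immediate hold avoids.** It avoids every dose in the table if the result is known before dosing. If a dosing-day result arrives after that day's dose, then in the *d* + 2 column it avoids 1 of 2 (day 1), 0 of 1 (day 2) and 1 of 1 (day 7).

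**Where scheduled tests fall.** The nominal FPG visits on days 8, 15, 22, 43, 64 and 85 are each one day after a multiple of 7, so all are block day 1. That day is also the trough. The previous dose was 144 h earlier, and at the stated half-life of about 40 h the fraction left is 2^(−144/40) = 0.08. The two-dose case may therefore be the less likely one.

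**Illustration of the second dose.** Assume one compartment, instant absorption and no carry-over from earlier blocks. Just after the day-2 dose time, exposure is 1 + 2^(−24/40) = 1.66 single-dose units if the dose is given and 0.66 if it is withheld, which is 1/1.66 = 60% lower. Over an assumed half-life range of 30 to 50 h, the reduction runs from 64% (1.57 v 0.57) to 58% (1.72 v 0.72).

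**The case against.** The best defence is that an earlier hold is already available. Section 7.2 says to interrupt first and to act on the worst preceding grade, and only the title of Table 4, not the body text, excludes hyperglycaemia. The Grade 4 rules in 12.6.1.1 are keyed to occurrence, with no two-day condition, and permission to restart presupposes a hold. Section 9.10 leaves room for physician decision. Appendix 6 is framed as recommendations, and the five days off limit further dosing after a peak.

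Much of this stands. It means the protocol does not clearly order continued dosing. It does not supply a threshold or a time: none of these clauses names a glucose level at which the next dose is withheld, and the one text that does address glucose says to continue until the two-day condition is met. The defence reduces the problem to an ambiguity without removing it.

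Two further points are accepted. The two-day wording on insulin does not forbid earlier insulin, so it is a weak default and not a prohibition. The wrong section number in Figure 3 is editorial.

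**Conclusion.** The gap is real but narrow. Appendix 6 has one glucose-based hold trigger, shared by Grades 3 and 4, and no stated immediate hold above 500 mg/dL. Under literal reading, its size is one or two further 140 mg doses for onset on or just before block days 1 and 2, and none for onset on days 3 to 5. That count assumes daily pre-dose FPG and glucose that stays high.

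A reader might infer three stronger things that the documents do not support:

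- **That sites are told to keep dosing at Grade 4.** The general wording in 7.2 and the restart wording in 12.6.1.1 permit a hold, so the instruction is unclear, not adverse.
- **That about half of the 29 planned patients are affected.** The figure of almost 50% is hyperglycaemia in all patients exposed to bimiralisib, not a Grade 4 rate on this schedule. No Grade 4 rate is given.
- **That ORR or the two-stage decision is biased.** Nothing in the documents shows an effect of this gap on either.

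This is a cheap safety clarification that is worth making.

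**What to change.** 1. In Section 12.6.1, directly after the instruction to continue while glucose is controlled, add: *Exception: if any FPG is > 500 mg/dL (27.8 mmol/L, G4), interrupt PQR309 at once regardless of duration and intensify anti-diabetic treatment; insulin need not wait two days once a laboratory value is > 500 mg/dL. The two-measurement confirmation does not delay this hold. If the laboratory confirms G4, restart follows the G4 rules of 12.6.1.1; if a home-glucometer value is not confirmed, manage the patient according to the laboratory value.*
2. In Figure 3, give Grade 4 its own row: *> 500 mg/dL, any duration: interrupt at once.* Leave the row for 250–500 mg/dL beyond two days as it is. Do not add a row telling sites to continue at 250–500 mg/dL for two days or less. Figure 3 is silent there and Section 7.2 supports interruption, so such a row could weaken care.
3. In Figure 3, replace section 10.8.2 with 12.6.1.1.

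The cost is amendment wording, an occasional unscheduled laboratory glucose test, and a few more holds and reductions to 100 mg. Those reductions are lasting: "Once the bimiralisib dose has been reduced, re-escalation is not permitted".

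One existing conflict would arise slightly more often. In the first three months, Section 7.2 makes a patient who cannot restart at 100 mg within 14 days not evaluable for the primary endpoint, while 12.6.1.1 lets a Grade 4 hold restart up to day 21. Section 7.2 should say whether the 14-day rule covers Appendix 6 holds that resolve on days 15 to 21.
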